### 2.3.2. Randomized telemedical and HCP sampling

After giving informed consent by signing the consent form, patients will be randomized to either OP+N GSS - or to OP+N USS.

After performing either procedure, they will continue to be sampled by HCP OP+N and HCP NP.

[figure not shown]
We will start the assessment with the self-sampling methods in order to reduce bias that could occur if they experience the HCP's sampling.

Written instructions on how to perform a self-test will be provided, representing the instructions that come along with a commercially available rapid test set. An instructional online video tutorial or similar would also account as the latest state of the art. However, this has not yet been implemented comprehensively with all available test sets that are currently being distributed across Switzerland.

Furthermore, to avoid bias in the sampling procedure, exclusively one HCP at the testing station will be designated as the study's sampling expert. The HCP will perform the NP and OP+N sampling sequentially in a previously randomized order.

The telemedical guidance will be exclusively done by the same HCP in order to minimize interoperability differences. The standardized telemedical sampling will be conducted at the same test station, in a separate empty room in which a computer will be placed with instructions on how to connect for the telemedical consultation.

Figure 1: Study chart

During each sampling procedure, the patients will either undergo OP+N GSS or OP+N USS for PCR analysis, as well as for antigenic testing. This means each participant will be sampled a total of six times within 15 minutes from different locations in the upper respiratory tract. Concordance of results between sampling by GSS vs. USS vs. HCPs will be assessed.

As the difference in time between the samplings can influence the Ct value, the sampling process will only be started when the HCP and the telemedical supervisor are ready. The three different samples will be stored in the test station refrigerator between 2°C-8°C before transport.

A grouping of samples will ensure that temperature changes are consistent between samples from the same participant.

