### 3.3 Study procedures

- The recruitment phase will start immediately after the approval of this study by the cantonal ethical committee.
- Sampling will be performed by a licensed and trained HCP.
- The telemedical supervision will be guided by a licensed medical doctor.
- The three different samplings will occur randomly in sequence (NP and OP+N by HCP and either OP+N USS or OP+N GSS by the participant)
- To ensure comparable results and reduce biases, all procedures will happen in the same testing premises. The HCP will always sample the participants. The same doctor will always guide the participants through self-sampling.
- Registration starts at least 24 hours before the telemedical consultation. The consultation will take about 10 minutes, sampling will take place at two time points, 15 minutes apart, and filling of the final questionnaire will take another 15 minutes. The rapid test result is announced immediately and the COVID-19 certificates will be issued according to cantonal guidelines. The PCR test evaluation takes a maximum of 24 hours and test results will be automatically communicated to the participant after analysis. Positive results and symptomatic people will be reported to the federal office of public health (FOPH) through the online reporting tool. The whole process from registration to the communication of the final PCR result will take approximately 48 hours for each patient.
- In case of a positive rapid test result, the FOPH is informed by the HCP on site through the online reporting system. In case of a positive PCR test, the FOPH and cantonal authorities are automatically informed by the analyzing laboratory.
- We aim to finalize the study by December 31st, 2022.
- Multiple laboratories have been contacted for participation in the study and the best fit is currently being evaluated.

Possible biases include mainly sampling bias and selection bias which are accounted for in the study design via randomization and through tight exclusion criteria. A list of possible confounders can be found in table 1 (Appendix).

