### 4.1.4. Statistical test

A variant of a paired student t test or Wilcoxon test (if non-normal distribution) with exchange of null and alternative (relaxed) hypotheses will be used as a non-inferiority test to assess differences in cycle threshold (Ct, considered as a log2-transformed measure of the amount of viral RNA load) between the NP and OP/N samples (HCP and GSS). Stratification for possible confounders will be done using logistic regression.

In order to show agreement between the approaches and estimate the limits of agreement and those are not too large, different graphical methods, such as Bland Altman diagrams will be used to show agreement between the approaches.

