## Appendix

### Schedule of assessments

Time	>-1 day	0	+1
Visit	Information	Testing	Results
oral and written Information	+		
Written consent		+	
check inclusion-/exclusion criteria		+	
Participant Characteristics		+	
Procedures		+	
Questionnaire		+	
Sampling		+	
Result communication		+	+ (PCR)

Shell Table 1: Potential confounders

Confounding Variables	Type of variable
Age	Continuous
Sex	Binomial
Mobility impairment	Nominal
Occupation	Categorical
Socioeconomic status	Continuous
Highest level of education attained	Ordinal

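### The randomised order of the two HCP procedures is left out of the paired NP versus OP+N analysis, which costs precision but does not bias the estimate

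*Combined protocol and SAP*

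**What the plan says.** Section 2.3.2 has each participant self-sample (GSS or USS by randomisation) and then undergo two procedures by the HCP. On those two: "The HCP will perform the NP and OP+N sampling sequentially in a previously randomized order". On the self-sample: "We will start the assessment with the self-sampling methods in order to reduce bias that could occur if they experience the HCP's sampling". Section 3.3 differs: "The three different samplings will occur randomly in sequence (NP and OP+N by HCP and either OP+N USS or OP+N GSS by the participant".

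The protocol treats timing as a possible influence: "As the difference in time between the samplings can influence the Ct value". It also notes that "each participant will be sampled a total of six times within 15 minutes from different locations in the upper respiratory tract", that is, three procedures with a PCR and an antigen swab at each.

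The analysis sections do not take this up:
- 4.1.1 describes randomisation for GSS versus USS only. The ratio and generation of the HCP order are not given.
- 4.1.2 stratifies by symptom status, age and sex, and 4.1.3 by viral load.
- 4.1.4 plans a paired t or Wilcoxon test of Ct, with logistic regression for possible confounders. No order, period or position term appears.
- The appendix table, "Shell Table 1: Potential confounders", lists age, sex, mobility impairment, occupation, socioeconomic status and education.

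**The concern.** All three hypotheses in 4.1.3 compare Ct values from the same person. A variable with the same value for both samples cancels from their difference. It may modify the difference, but it cannot confound it, and this is true of every entry in the appendix table. What does differ between two samples of one person is when each was taken and what was sampled before it. The trial randomises this for the HCP procedures and then does not use it.

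At stake are the width of the NP versus OP+N interval and the chance to report a randomised estimate of how an earlier procedure changes the Ct of a later one. Readers would want that estimate when judging the self-sample comparisons.

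**Working it through.** **Inputs from the documents (4.1.2):** margin 3 Ct; variability 6 (called a standard error, but it works as an SD); one-sided 97.5% interval; power 90%; 85 per group, so 170 people.

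**The plan's own figure.** n per group = 2 × [6 × (1.960 + 1.282)/3]² = 84.06, so 85. It reproduces, using the formula for two independent groups with 6 read as an SD.

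**Assumed inputs (not in the documents):** d, the Ct step from the second to the third procedure, 1 or 2; s, the SD of the paired difference, 3, 6 or 8.49. The last is 6 × √2, which applies if 6 is the SD of a single measurement and the two are uncorrelated.

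**Model.** Let D = NP minus OP+N by HCP and code order as o = +1 if NP came last, −1 if OP+N came last. Then D = μ + d·o + error with SD s. With the two orders equally likely, o averages zero, so the plain mean of D is unbiased for μ. The SD of D without an order term is sqrt(s² + d²), so the reported standard error is inflated by sqrt(1 + d²/s²).

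| s | d | SE without order, sqrt((s²+d²)/170) | SE with order, s/sqrt(170) | Inflation |
|---|---|---|---|---|
| 3 | 1 | 0.2425 | 0.2301 | 5.4% |
| 3 | 2 | 0.2765 | 0.2301 | 20.2% |
| 6 | 1 | 0.4665 | 0.4602 | 1.4% |
| 6 | 2 | 0.4851 | 0.4602 | 5.4% |
| 8.49 | 1 | 0.6553 | 0.6508 | 0.7% |
| 8.49 | 2 | 0.6686 | 0.6508 | 2.7% |

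**Chance imbalance.** Under simple randomisation it moves the unadjusted mean by a random amount with SD d/sqrt(170): 0.08 Ct for d=1 and 0.15 for d=2. This is already inside s² + d² and must not be counted again.

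**Order effect.** Half the difference between the two order-specific means estimates d, with SE s/sqrt(170) = 0.23 (s=3) to 0.46 (s=6). This needs a Ct pair from all 170 people, as for the housekeeping gene. For viral genes only positives contribute: at an assumed 20% positivity there are 34 pairs, and the SE is 3/√34 = 0.51 to 6/√34 = 1.03.

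**Person-level covariates.** In 4,000 simulated trials (170 people, orders split 85:85, s=6, d=2, no true method difference), the mean NP minus OP+N was 0.006 with or without centred age and sex terms.

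**Self-sample contrasts.** If the self-sample is always first and each later procedure adds d, HCP OP+N is shifted by d in half the people and 2d in the other half, on average 1.5d. In the same simulation (d=2, so 3.0 expected), HCP OP+N minus self was 2.995 unadjusted, 2.995 with age and sex, and 2.995 with HCP order also included. The order term does not touch this shift.

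**The case against.** The strongest reply is that randomising the order already does the work: the NP versus OP+N estimate is unbiased and the paired interval valid. That stands. A reader might infer that leaving order out biases this comparison, or that chance imbalance becomes bias; the documents do not support this, since the imbalance is random error that the paired standard error already covers. At s=6 and 170 pairs, power against the margin of 3 exceeds 99.9% with or without the term, so no conclusion of the trial is likely to turn on it.

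A second reply is that the term does not reach the more vulnerable comparisons. That also stands. A reader might infer that it would correct the self-sample versus HCP contrasts. With the self-sample always first, position and method cannot be separated there.

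A third is that the confounder list serves the study as a whole. This is fair. Section 2.1 includes GSS versus USS, a between-person comparison, and the primary endpoint in 2.2 is antigen concordance, which is binary and suits a logistic model. The variables can also modify a within-person difference. The appendix table is therefore not useless; it merely contains nothing that can confound a within-person contrast.

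What remains is that the plan randomises a factor because it may matter and then does not analyse by it.

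**Conclusion.** The point holds as a modest one about precision and reporting. Omitting the randomised order widens the NP versus OP+N interval by 1.4% to 5.4% at s=6 for a step of 1 to 2 Ct; only the combination s=3, d=2 reaches 20%. It does not bias the estimate.

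This rests on assumed values of d and s, on the two orders being equally likely (the ratio is not stated), and on the step being the same whichever procedure comes first. If the orders are exactly balanced, the estimate itself is no more variable without the term; it is the reported interval that is wider than it need be.

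The position confounding in the self-sample contrasts follows from the sequence in 2.3.2 and would remain after the change. Its size is unknown: 1.5 Ct, half the margin, if each later procedure raised Ct by 1. It would favour non-inferiority if later samples have higher Ct and work against it if lower. If the fully random sequence in 3.3 is what governs, position varies for the self-sample too and could be modelled.

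**What to change.** 1. Reconcile 2.3.2 (self-sample first) with 3.3 (all three in random sequence) before defining any position term.
2. State how the HCP order is generated and in what ratio, and record for each participant the order actually followed.
3. In 4.1.4, analyse NP versus OP+N by HCP with procedure order as a fixed factor, so that the estimate is the mean of the two order-specific mean differences. Report the estimated order effect with its interval and the number of Ct pairs behind it, separately for the housekeeping and viral genes.
4. As a sensitivity display, report self minus HCP OP+N separately by whether HCP OP+N was the second or third procedure. State that this does not remove the confounding of position with method.
5. For the within-person contrasts, describe the appendix variables as possible effect modifiers; keep them as covariates for GSS versus USS.

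The cost is one degree of freedom, one recorded item per participant and a few lines of SAP text. No extra participants or swabs are needed.

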### 3 PROJECT POPULATION AND STUDY PROCEDURES

#### 3.1 Project population, inclusion and exclusion criteria

All patients, regardless of symptoms, who present themselves at the Test-station SARS-CoV-2 testing will be offered to participate in the study.

Study inclusion criteria;

- Written informed consent
- Patients visiting the test-station for a SARS-CoV-2 test
- Consent to comply with the study protocol
- Age of 18 or older

List the study exclusion criteria:

- Refusal to comply with the study protocol
- Digital illiteracy (i.e. patients who would never use telemedicine as they do not feel competent enough to use the necessary tools)
- Not German or English speaking
- People trained in the use of rapid diagnostic tests (HCP, biologists) will be excluded to reduce bias

#### 3.2 Recruitment, screening and informed consent procedure

The participating test station in Olten receives approximately 100 patients per day for PCR and/or antigen testing. The population is mixed as both asymptomatic people, as well as symptomatic people, frequent the facility for SARS-CoV-2 testing. The recruitment will happen by the local investigator in daily clinical practice. All costs for tests performed within the framework of the study will be financed by the study. A payable travel certificate will be issued for unchanged costs. Participation in the study and spending time on it is voluntary, free of charge and at no cost to the study participants. However, each study participant will receive a voucher for free PCR testing at a later date.

Patients who wish to have a COVID test can register online at least one day in advance for predefined time slots for appointments (via the Onedoc-Software, Geneva, Switzerland).

Immediately after registration, the potential test participants will be informed about the study either by telephone or by e-mail based on their contact details, with delivery of the written study material if they are interested, giving them more than 24 hours to contemplate whether they want to participate.

At the consultation, a personal oral and written briefing about the study goals and study design, as well as the informed consent form will be given to the participants. They are invited to date and sign if they are willing to participate and have no further questions, and express to have understood the content and do agree with it. A copy of the signed document will be given to the study participant. The consent form will be stored as part of the study records.

Participants will not receive financial compensation for the participation in this study. However, each study participant will receive a voucher for free PCR testing at a later date.

We shall end recruiting either when reaching the necessary sample size or no later than October 30th, 2022.

### 3.3 Study procedures

- The recruitment phase will start immediately after the approval of this study by the cantonal ethical committee.
- Sampling will be performed by a licensed and trained HCP.
- The telemedical supervision will be guided by a licensed medical doctor.
- The three different samplings will occur randomly in sequence (NP and OP+N by HCP and either OP+N USS or OP+N GSS by the participant)
- To ensure comparable results and reduce biases, all procedures will happen in the same testing premises. The HCP will always sample the participants. The same doctor will always guide the participants through self-sampling.
- Registration starts at least 24 hours before the telemedical consultation. The consultation will take about 10 minutes, sampling will take place at two time points, 15 minutes apart, and filling of the final questionnaire will take another 15 minutes. The rapid test result is announced immediately and the COVID-19 certificates will be issued according to cantonal guidelines. The PCR test evaluation takes a maximum of 24 hours and test results will be automatically communicated to the participant after analysis. Positive results and symptomatic people will be reported to the federal office of public health (FOPH) through the online reporting tool. The whole process from registration to the communication of the final PCR result will take approximately 48 hours for each patient.
- In case of a positive rapid test result, the FOPH is informed by the HCP on site through the online reporting system. In case of a positive PCR test, the FOPH and cantonal authorities are automatically informed by the analyzing laboratory.
- We aim to finalize the study by December 31st, 2022.
- Multiple laboratories have been contacted for participation in the study and the best fit is currently being evaluated.

Possible biases include mainly sampling bias and selection bias which are accounted for in the study design via randomization and through tight exclusion criteria. A list of possible confounders can be found in table 1 (Appendix).

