## 2.2 Primary and secondary endpoints

The Ct-value is defined as the number of cycles required for a signal to cross the detection threshold and can be used as a surrogate for sampling quality, as it allows to quantify the amount of material that is being extracted.

Primary endpoints:

- Concordance of positive/negative samples in antigen tests with GSS, USS, and HCP-based samples.

Secondary endpoints:

- Housekeeping gene Ct comparison based on sampling method between samples based on GSS, USS, or HCP
- ORF1ab/RdRp-, E-, N-, and S genes Ct value comparison based on sampling method between samples based on GSS, USS, or HCP
- Qualitative analysis of perceived sampling accuracy established with a short form
- Detected variant of concern
- Case report form (CRF) assessing basic demographics and variables of interests as indicated separately in the CRF form
- Prevalence of variants of concern
- Immunization status
- Travel destinations in the passed three months
- n of people in which a nasopharyngeal sampling is possible correctly (ratio)

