## 8 FUNDING / PUBLICATION / DECLARATION OF INTEREST

This project is privately funded by the local investigator, Dr. med. [name].

There is a conflict of interest between one of the investigators (Dr. med. [name], CEO of GobiX GmbH) who has a remote diagnostics startup and provides the testing facilities.

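### No masking is specified for the antigen reader, the single HCP sampler or the PCR laboratory, so the paired antigen concordance endpoint can be biased, most plausibly upward

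*Combined protocol and SAP*

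**What the plan says.** All references are to the combined protocol and SAP.

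- **Endpoint.** Section 2.2 gives the primary endpoint as "Concordance of positive/negative samples in antigen tests with GSS, USS, and HCP-based samples". It states no agreement statistic, margin or success threshold.
- **Data per person.** Section 2.3.2 has six samples per participant, for PCR and for antigen testing, from three procedures (self, HCP OP+N, HCP NP). That is 6/2 = 3 antigen results per person.
- **Handling on site.** Section 3.3: "The rapid test result is announced immediately and the COVID-19 certificates will be issued according to cantonal guidelines". It adds: "In case of a positive rapid test result, the FOPH is informed by the HCP on site through the online reporting system".
- **Sampler.** Section 2.3.2: "exclusively one HCP at the testing station will be designated as the study's sampling expert". That person takes both comparator swabs.
- **Guide.** Section 2.3.2: "The telemedical guidance will be exclusively done by the same HCP in order to minimize interoperability differences". Section 3.3: "The telemedical supervision will be guided by a licensed medical doctor".
- **Order and timing.** Section 2.3.2 puts self-sampling first and all six samples within 15 minutes. Section 3.3 puts all three samplings in random sequence, at two time points 15 minutes apart.
- **Bias controls.** Section 3.3 relies on randomization and the exclusion criteria. Section 4.1.1 adds sealed opaque envelopes, opened just before swabbing.

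Masking of the swab taker, antigen reader, PCR laboratory or analyst is not mentioned.

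**The concern.** Concordance is informative only if the paired results are obtained independently. Three results from one person arise at the same station in one visit, and nothing stops one reader from seeing all three and knowing which method produced each. An equivocal result may then be settled in the light of the others. The endpoint would partly measure the reader's consistency instead of sampling quality, and this cannot be undone at analysis.

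The second route is the comparator swab. Using one HCP removes variation between operators, but not that operator's knowledge of whether the participant has just been guided or left unsupervised. If swabbing effort varies with that knowledge, the yardstick differs between arms, for Ct as well as for antigen. The envelopes do not help here: they protect the assignment up to the moment of opening and mask nobody afterwards.

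**Working it through.** **1. The plan's own figure.** Section 4.1.2 gives 85 per group: margin 3 Ct, true difference 0, one-sided 2.5%, power 90%. Reading its variability of 6 as an SD:

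n = 2 × 6² × (1.960 + 1.282)² / 3² = 8 × 10.51 ≈ 84.1, rounded up to 85 per group.

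The figure reproduces, with power 90.3% at 85. The variable is Ct, not the antigen result, and sections 4.1.3 and 4.1.4 test Ct as well. Antigen reading therefore does not enter the non-inferiority test.

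**2. Effect of non-independent readings on concordance.** The documents give no expected agreement, so these inputs are assumed: 20% HCP-positive, positive agreement p of 60% or 80%, negative agreement 99%. Let a share f of discordant pairs be read so that the self-sample matches the HCP sample. Then

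positive agreement = p + f × (1 − p).

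| f | p = 60% | kappa | p = 80% | kappa |
|---|---|---|---|---|
| 0 | 60% | 0.68 | 80% | 0.84 |
| 10% | 64% | 0.72 | 82% | 0.86 |
| 25% | 70% | 0.77 | 85% | 0.88 |
| 50% | 80% | 0.85 | 90% | 0.92 |

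For example, 0.60 + 0.25 × 0.40 = 0.70. Positive agreement does not depend on the share HCP-positive. With 10% or 40% HCP-positive, the rise in kappa is similar.

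The opposite direction is possible. If a reader expecting poor self-swabs read 10% of concordant positive pairs as discordant, 60% would fall to 0.60 × 0.90 = 54%.

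**3. Effect of swabbing effort on Ct.** With SD 6 and 85 per group, SE = 6 × √(2/85) = 0.92. Section 4.1.3 tests HCP Ct minus GSS Ct against −3. Suppose lower HCP effort raises HCP Ct by b. The one-sided type I error at a true difference of −3 is Φ(b/SE − 1.96):

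| b (Ct) | type I error |
|---|---|
| 0 | 2.5% |
| 0.25 | 4.6% |
| 0.5 | 7.8% |
| 1.0 | 19.1% |

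Section 4.1.4 plans a paired test. If 6 were the SD of paired differences, SE = 6/√85 = 0.65, and the last three rows become 5.8%, 11.7% and 33.6%. A bias that lowers HCP Ct takes the error below 2.5%. The values of b are illustrations; the documents give no basis for any of them.

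**4. Can the sampler be masked?** Section 2.3.2 can be read as making the sampler and the guide one person; section 3.3 describes a doctor as guide. If they are one person, the sampler knows the arm of every guided participant and, by elimination, of the others. If they are two, masking is feasible, and the separate room in section 2.3.2 already supports it.

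**The case against.** The strongest reply is that silence is not a defect. Section 2.1 refers to an attached SOP, and section 7.1 promises strict SOPs against bias. Labelling and reading steps may be set out there, and that document was not available. This stands as a limit: the point concerns the protocol text, which should then cite the SOP.

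Section 2.3.2 also has safeguards: a separate room for telemedical sampling, and self-sampling first. Under that order, the HCP's swabs cannot influence the self-swab. Section 3.3's random order contradicts this, and neither safeguard concerns reading.

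Four stronger readings are tempting, and the documents do not support them:

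- *Unmasked antigen reading favours non-inferiority.* It cannot under this plan, since the margin, hypotheses and test are all on Ct.
- *The tests are read by eye, with the paired results in view.* The reader and the reading method are not stated. Informing the FOPH of a positive is reporting, not reading.
- *Immediate announcement causes the bias.* Announcing a result does not alter a reading already made. Nothing says that one result is announced before the others are read.
- *The declared interest shows bias.* Section 8 discloses an investigator "who has a remote diagnostics startup and provides the testing facilities", but not that this person swabs or reads tests. It makes masking more desirable and proves nothing.

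**Conclusion.** The point holds as a gap with an inexpensive remedy. Followed as written, the plan permits non-independent antigen readings on its stated primary endpoint and a comparator sampler who knows the arm. An upward bias in concordance is the most plausible direction, but it is a risk and not a demonstrated effect. Its size rests wholly on the assumed share of discordant pairs resolved: from 60% true positive agreement, 4 to 20 percentage points over the range shown; from 80%, 2 to 10 points.

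For Ct, the only route is HCP effort that varies with a known arm. Its direction is open and its size unknown. The 85 per group is unaffected. The change should be made before recruitment.

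**What to change.** In section 3.3, with matching SOP wording:

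1. Label antigen devices and PCR tubes with the study number plus a random code, not the method.
2. Record each antigen result at the kit's reading time before the next device is seen, with a photograph if the device is read by eye. Where two team members are present, the one who did not take that swab reads it.
3. Announce results only after all three readings are locked.
4. Reconcile sections 2.3.2 and 3.3 on swab order, timing and whether guide and sampler are the same person. If they are different people, have the self-swab done out of the sampler's sight and the envelope opened by someone other than the sampler. If they are the same person, state that the sampler is unmasked and report this as a limitation.

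The cost is protocol and SOP wording, coded labels and possibly a photograph per device, with no extra staff. Results are announced a few minutes later, and a participant may occasionally reveal the arm to the sampler.
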